8.4 IMMUNOGENICITY ASSESSMENTS

Venous blood samples for the determination of immune responses will be collected at the time points indicated in the TIME AND EVENTS SCHEDULE. Serum samples will be shipped to Q2 Solutions laboratory for analysis of binding antibodies against EBOV GP using the FANG ELISA.

Sample collection and processing will be performed by the study-site personnel according to current versions of approved standard operating procedures. The Laboratory Manual contains further details regarding the collection, handling, labeling, and shipment of blood samples to the relevant laboratories.

8.4.1 Future scientific research

Future scientific research may be conducted to further investigate Ebola vaccine- and disease-related questions and to study other infections of public health importance in the host countries and neighbouring countries. This may include the development of new, or the improvement of existing, techniques to characterise EBOV-directed immune responses or other diagnostic tests. No additional samples will be taken for these analyses, however, residual samples from the study tests may be retained for these purposes and analysed after the end of the study.

8.5 SAMPLE COLLECTION AND HANDLING

The actual dates and times of sample collection must be recorded in the CRF or laboratory requisition form.

Refer to the TIME AND EVENTS SCHEDULE for the timing and frequency of all sample collections.

Instructions for the collection, handling, storage, and shipment of samples are found in the Laboratory Manual that will be provided. Collection, handling, storage, and shipment of samples must be under the specified, and where applicable, controlled temperature conditions as indicated in the Laboratory Manual.

9 PARTICIPANT COMPLETION/WITHDRAWAL FROM THE STUDY

9.1 COMPLETION

A participant will be considered to have completed the study if he or she has completed all assessments at the 28 day post-vaccination visit (Day 29).

Participants who prematurely discontinue study intervention for any reason before completion of the 28 day post-vaccination visit will not be considered to have completed the study

9.2 WITHDRAWAL FROM THE STUDY

A participant has the right to withdraw from the study at any time for any reason. The investigator should make an attempt to contact participants who did not return for scheduled visits. Although a participant is not obliged to give reason(s) for withdrawing prematurely, the investigator should make a reasonable effort to ascertain the reason(s) while fully respecting the participant's rights.

A participant will be withdrawn from the study for any of the following reasons:

- Lost to follow-up
- Withdrawal of consent
- Death
- Repeated failure to comply with protocol requirements
- Decision by the sponsor or the investigators to stop or cancel the study

Decision by local regulatory authorities or IEC/IRB to stop or cancel the study

If a participant is lost to follow-up, every reasonable effort must be made by the study-site personnel to contact the participant and determine the reason for discontinuation/withdrawal. The measures taken to follow up must be documented.

When a participant withdraws before completing the study, the reason for withdrawal, if given, is to be documented in the CRF and in the source document.

A participant who wishes to withdraw consent will be offered an optional visit for safety follow-up (before the formal withdrawal of consent). The participant has the right to refuse this optional visit.

Withdrawal of Consent for the Use of Samples in Future Research

A participant may withdraw consent for use of samples for research (refer to Section 15.2.5). In such a case, every possible effort will be made to destroy samples after they are no longer needed for the study. Details of the sample retention for research are presented in the ICF.

10 STATISTICAL METHODS

Statistical analysis will be done by the sponsor or under the authority of the sponsor. A general description of the statistical methods to be used to analyse the safety and immunogenicity data is outlined below. Specific details will be provided in the Statistical Analysis Plan.

The final analysis will be performed at study completion, defined as the date of the final database lock, which will occur after all participants have completed the last study-related visit or left the study.

10.1 ANALYSIS SETS

Full Analysis Set: The full analysis set will include all participants with study intervention administration documented. This will be used for safety analysis.

Per-protocol Immunogenicity Population: The per-protocol immunogenicity population will include all vaccinated participants for whom immunogenicity data are available excluding participants with major protocol deviations expecting to impact the immunogenicity outcomes.

10.2 SAMPLE SIZE DETERMINATION

Approximately 50 HIV positive adult participants are expected to be enrolled into this trial. This number is based on the potentially available HIV positive participants who previously received the 2-dose Ebola vaccine regimen (Ad26.ZEBOV followed by MVA-BN-Filo) at sites in Kenya and Uganda.

10.3 PARTICIPANT INFORMATION

For all participants, demographic characteristics (e.g., age and sex), and other baseline characteristics (e.g. vital signs) will be tabulated and summarised with descriptive statistics.

10.5 IMMUNOGENICITY ANALYSIS

Graphical representations of immunological parameters will be made as applicable. Frequency tabulations will be calculated for discrete (qualitative) immunologic parameters as applicable.

10.6 INTERIM ANALYSIS

No interim analysis will be performed for this study.

10.7 INDEPENDENT DATA MONITORING COMMITTEE

An Independent Data Monitoring Committee (IDMC) will not be appointed for this study. The safety of the Ad26.ZEBOV vaccine has already been shown in HIV positive adults in previous studies. A booster dose of Ad26.ZEBOV was also shown to be safe in HIV negative adults. There are no planned interim analyses. Thus the IDMC's role will be designated to an independent medical reviewer. The independent medical reviewer will be identified by the sponsor to review the accumulating safety data on an ongoing basis to ensure the continuing safety of the participants enrolled in this study.

The independent medical reviewer will be consulted periodically to review newly generated data. Ad hoc meetings may be requested via the sponsor if any of the pre-specified pausing rules for this study are met (see Section 8.3.2) or in any situation that could affect the safety of the participants.

After the review, the independent medical reviewer will make recommendations regarding the continuation of the study. The independent medical reviewer responsibilities, authorities, frequency and timing of the evaluations and procedures will be documented in a role and responsibility description.

The independent medical reviewer will be external and independent of the sponsor. He or she will be a medical expert in the relevant field.

11 ADVERSE EVENT REPORTING

Timely, accurate, and complete reporting and analysis of safety information from clinical studies are crucial for the protection of participants, investigators, and the sponsor, and are mandated by regulatory agencies worldwide. The sponsor has established standard operating procedures in conformity with regulatory requirements worldwide to ensure appropriate reporting of safety information; all clinical studies conducted by the sponsor or its affiliates will be conducted in accordance with those procedures.

Method of Detecting Adverse Events and Serious Adverse Events

Care will be taken not to introduce bias when detecting AEs or SAEs. Open-ended and nonleading verbal questioning of the participant is the preferred method to inquire about AE occurrence.

Solicited Adverse Events

Solicited AEs are predefined local (at the injection site) and systemic events for which the participant is specifically questioned, and which are noted in the participant's diary.

Unsolicited Adverse Events

Unsolicited AEs are all adverse events for which the participant is not specifically questioned in the participant diary.

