Safety and immunogenicity of an Ad26.ZEBOV booster vaccine in Human Immunodeficiency Virus Positive (HIV+) adults previously vaccinated with the Ad26.ZEBOV, MVA-BN-Filo vaccine regimen against Ebola: a single-arm, open-label Phase II clinical trial in Kenya and Uganda.

SUPPLEMENTARY MATERIAL

Table of Contents

1.	Supplementary Tables	. 1
	Table S1. Participant haematology and HIV assessments at screening for enrolment	. 1
	Table S2. Unsolicited adverse events summary	2
2.	EBL2010 Study Group.	. 2
3.	Study Protocol.	. 8

1. Supplementary Tables

Table S1: Participant haematology and HIV assessments at screening for enrolment. Full blood count, CD4+ T cell count, and HIV viral load measurement were performed by local laboratories at the screening visit, within 28 days prior to booster vaccination.

Full analysis set	Total (N=26)
Haemoglobin, g/dl	
Mean (SD)	14.1 (1.4)
Median (Q1; Q3)	14.1 (11.3; 16.8)
WBC, \times 10 9 /L	
Mean (SD)	5.5 (1.4)
Median (Q1; Q3)	5.1 (2.8; 9.8)
Low WBC ¹ , n (%)	1(4)
LYM, \times 10 ⁹ /L	
Mean (SD)	2.6 (0.6)
Median (Q1; Q3)	2.4 (1.6; 4.6)
$MON, \times 10^9/L$	
Mean (SD)	0.4 (0.1)
Median (Q1; Q3)	0.3 (0.1; 0.7)
Low MON ¹ , n (%)	1(4)
$GRA, \times 10^9/L$	
Mean (SD)	4.8 (0.5)
Median (Q1; Q3)	4.7 (4.0; 5.6)
Platelets, \times 10 ⁹ /L	
Mean (SD)	265.4 (61.1)
Median (Q1; Q3)	259.0 (190.0; 494.0)
CD4 count, cells/μL ²	
Mean (SD)	808.8 (175.3)
Median (Q1; Q3)	828 (519; 1130)
HIV viral load, copies/mL	
Not detected, n (%)	13 (50)
< 40, n (%)	12 (46)
45, n (%)	1 (4)

Granulocytes (GRA); lymphocytes (LYM); monocytes (MON); first quartile (Q1); third quartile (Q3); standard deviation (SD); white blood cells (WBC).

¹Classified according to age and sex specific normal ranges of the local laboratory.

Table S2. Unsolicited adverse events summary

Full analysis set	Total (N = 26)
	n (%)
Unsolicited adverse events (AEs),	12 (46)
Infections and infestations	5 (19)
Upper respiratory tract infection	3 (12)
Urinary tract infection	2(8)
Otitis media	1 (4)
Vaginal candidiasis	1 (4)
Gastrointestinal disorders	2 (8)
Acute gastritis	1 (4)
Gastroesophageal reflux disease	1 (4)
Nervous system disorders	2 (8)
Headache	2 (8)
Musculoskeletal and connective tissue disorders	2 (8)
Low back pain	2 (8)
Neck pain	1 (4)
Metabolism and nutrition disorders	2 (8)
Diabetes	1 (4)
Anorexia	1 (4)
Blood and lymphatic system disorders	1 (4)
Lymphadenopathy axillary	1 (4)
Cardiac disorders	1 (4)
Chest heaviness	1 (4)
Vascular disorders	1 (4)
Diastolic hypertension	1 (4)

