After vaccination, participants will remain under observation at the study site for at least 30 minutes for surveillance for any acute reactions, or longer if deemed necessary by the investigator. Symptoms of solicited local (at the injection site) and systemic AEs will be collected in the diary in the evening after the vaccination and then daily for the next 7 days. Diaries will be completed at home by the participant on the day of vaccination (Day 1) and daily for the next 6 days. Day 8 of the diary will be completed by study site staff at the clinic. Diary information will be transcribed by the study personnel into the diary CRF pages. Once a solicited symptom from a diary is considered to be of severity Grade 1 or above, it will be referred to as a solicited AE.

Solicited Injection Site (Local) Adverse Events

Participants will be asked to note in the diary occurrences of tenderness, erythema and swelling at the study intervention injection site on the day of vaccination and daily for the subsequent 6 days. The extent (largest diameter) of any erythema, and swelling should be measured (using the ruler supplied) and recorded daily. Day 8 of the diary will be completed by study staff at the site clinic.

Injection Site Tenderness

Injection site tenderness is a painful sensation localised at the injection site upon palpation or movement of the limb. Due to subjective nature of the reaction, the severity assessment of tenderness is self-reported (if a participant is unable to provide self-report, other reporters include care giver or health care provider).

• Injection Site Erythema

Injection site erythema is a redness of the skin caused by dilatation and congestion of the capillaries localised at the injection site. It can best be described by looking and measuring.

• Injection Site Swelling

Injection site swelling is a visible enlargement of the site injection. It may be either soft (typically) or firm (less typical).

Itching

This refers to the local itching at the site of injection.

Note: Any other injection site events not meeting the above case definitions should be reported separately as unsolicited AEs.

Solicited Systemic Adverse Events

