11.3.1 All Adverse Events

Symptoms of solicited local and systemic AEs will be collected in the diary in the evening after the vaccination and then daily for the next 7 days. Unsolicited AEs will be reported from vaccination until 28 days post-vaccination.

Serious adverse events and/or special reporting situations that are related to study procedures will be reported from the time a signed and dated ICF is obtained onwards until the end of the study. All other SAEs and/or special reporting situations will be reported from the day of vaccination onwards until 28 days post-vaccination. The sponsor will evaluate any safety information that is spontaneously reported by an investigator beyond the time frame specified in the protocol.

The investigator will monitor and analyse the study data including all AEs and clinical laboratory data as they become available and will make determinations regarding the severity of the adverse experiences and their relation to study intervention. All AEs will be deemed related to study intervention or not related to study intervention, according to Section 11.1.2.

The investigator or clinical designee must review both post-injection reactogenicity and other adverse event CRFs to insure the prompt and complete identification of all events that require expedited reporting as SAEs, invoke pausing rules, or are other serious and unexpected events.

All AEs, regardless of seriousness, severity, or presumed relationship to study intervention, must be recorded using medical terminology in the source document and the CRF. Whenever possible, diagnoses should be given when signs and symptoms are due to a common etiology (e.g., cough, runny nose, sneezing, sore throat, and head congestion should be reported as "upper respiratory infection"). Investigators must record in the CRF their opinion concerning the relationship of the AE to study therapy. All measures required for AE management must be recorded in the source document and reported according to sponsor instructions.

The LSHTM assumes responsibility for appropriate reporting of AEs to the regulatory authorities. The LSHTM will also report to the vaccine manufacturer and investigator (and the head of the investigational institute where required) all SUSARs. The investigator (or sponsor as required) must report SUSARs to the appropriate IEC/IRB that approved the protocol unless otherwise required and documented by the IEC/IRB.

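### Injection-site itching is defined as a solicited local event, but neither the diary instruction nor the Day 8 site examination asks about it

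*Combined protocol and SAP*

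**What the plan says.** Safety and tolerability of the booster is one of the two objectives in Section 2.1, and the Synopsis calls it primary. Section 8.3.1, under solicited injection-site events, gives separate definitions for tenderness, erythema, swelling and itching. The itching entry reads: "This refers to the local itching at the site of injection". The Note closing that list reads: "Any other injection site events not meeting the above case definitions should be reported separately as unsolicited AEs".

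The diary instruction that opens the same list reads: "Participants will be asked to note in the diary occurrences of tenderness, erythema and swelling at the study intervention injection site". Section 8.1.3 describes the injection-site examination at the Day 8 visit and names the same three signs. The systemic diary items in Section 8.3.1 do not include itching.

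Section 11 separates the two classes by what is asked. Solicited events are predefined ones "for which the participant is specifically questioned, and which are noted in the participant's diary". For the other class: "Unsolicited AEs are all adverse events for which the participant is not specifically questioned in the participant diary". Timing is given in Section 11.3.1: "Symptoms of solicited local and systemic AEs will be collected in the diary in the evening after the vaccination and then daily for the next" seven days, with unsolicited events reported until 28 days after vaccination. Section 8.3.1 adds: "Day 8 of the diary will be completed by study site staff at the clinic".

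**The concern.** A solicited rate can be interpreted because every participant is asked about the same item on the same days. If an item is called solicited but nobody is prompted for it, a blank can mean either no itching or itching not mentioned. The rate is then tabulated beside tenderness, erythema and swelling as if collected in the same way, and it is biased downwards. Section 1.2.3 names local itching first among the expected effects of intramuscular injection and says the listed risks will be monitored, so this is an event the protocol meant to capture.

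Class also has consequences. Under Section 11.1.2 a solicited local event is related to the vaccine by definition, whereas an unsolicited one needs a causality judgement. Under Section 11.1.3 the modified DAIDS table grades events other than solicited ones. Two sites following different sections could handle the same volunteered itch differently.

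**Working it through.** The plan states no figure on this point, so the check is mainly a comparison of passages.

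| Place in the protocol | Itching is asked about or examined | Class that follows for itching |
|---|---|---|
| 8.3.1, itching entry | not addressed | solicited |
| 8.3.1, Note | not addressed | not unsolicited, because it meets a listed definition |
| 8.3.1, diary instruction | no (tenderness, erythema, swelling) | not stated |
| 8.3.1, systemic list | no | not stated |
| 8.1.3, Day 8 examination | no (erythema, swelling, tenderness) | not stated |
| 11, solicited definition | requires questioning and a diary entry | not solicited if not asked |
| 11, unsolicited definition | everything the diary does not ask about | unsolicited if not asked |
| 1.2.3 | listed among the risks to be monitored | not stated |

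1. *Class.* The first two rows make itching solicited. If the diary follows its written instruction, the two Section 11 rows make it unsolicited. Both cannot hold.

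2. *Ascertainment.* No row with a collection procedure names itching, so on the written text it is recorded only if volunteered or noticed.

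3. *Direction and size.* Let p be the true proportion with itching and s the chance that an unprompted participant reports it. The expected recorded rate is p × s, and the shortfall is p × (1 − s). The documents give neither p nor s. Across the whole range of s, the shortfall runs from 0 (s = 1) to p (s = 0). Each participant missed lowers the rate by 1/26 = 3.8 percentage points at the 26 analysed, or 1/50 = 2.0 points at the planned 50.

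4. *Can the results settle it?* "Table S2. Unsolicited adverse events summary", as supplied, shows no injection-site event, and the documents contain no table of solicited events from this trial. That fits a diary that asked about itching, with any cases counted as solicited. It also fits a diary that did not ask, with no case volunteered. The results do not decide between them.

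**The case against.** The strongest reply is that Section 11 already resolves the matter: if the diary asks about itching it is solicited, and if it does not, itching is unsolicited, so nothing goes unclassified. The diary is also a separate study supply (Section 14) that is not in the documents and may well have an itching line. The second half stands, so the finding concerns the protocol text and not what participants were actually asked. The first half does not remove the conflict, because the Section 8.3.1 Note gives the opposite class. Nor does it supply the missing question.

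A reader might also infer more from the Section 11 definitions, in three ways that the documents do not support:

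- *Diary-type symptoms starting on Days 9 to 29 belong to neither class, or are dropped.* Unsolicited is the residual class. A headache on Day 15 is an event the diary did not ask about, so it is unsolicited on the plain words. Section 11.3.1 gives both collection windows and requires every adverse event to be recorded, and Section 10.4 analyses all onsets within 28 days. The 29 − 8 = 21 days after the diary closes are a length of time, not a count of errors.
- *Table S2 breaks the written rule by listing headache, a diary item, in 2 of 26 participants.* The table gives no onset dates, and headaches starting after Day 8 would belong there.
- *Tenderness must be relabelled as pain to match Table 1.* Section 8.3.1 defines tenderness as a painful sensation on palpation or movement, and its Note sends other local events to the unsolicited class. Table 1 pools other studies, and nothing requires identical labels.

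**Conclusion.** The point holds for itching. The protocol defines it as solicited, keeps it out of the unsolicited class through the Note, and names it in neither the diary instruction nor the Day 8 examination. If the written procedure was followed, a solicited itching rate would be under-ascertained. The direction is clear, but the size is unknown.

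This rests on two assumptions: that the diary form matches the protocol's list, and that some participants with itching would not mention it unprompted. If the form did ask about itching, the defect is limited to wording and the data are sound. It should not be inferred that itching was in fact missed in this trial.

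The missing onset window in the Section 11 definitions is a matter of clarity only. It leaves no event unrecorded or unanalysed.

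**What to change.** 1. Reconcile Sections 8.3.1 and 8.1.3 by adding itching to the diary's local symptom list and to the Day 8 assessment. This fits the intention in Section 1.2.3 to monitor it. It costs a word or two in two sentences and one diary line.

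2. A diary item cannot be added retrospectively for the 26 participants already reported. For them, check the diary form and state whether it asked about itching. If it did, say so in a footnote to the solicited table. If it did not, report any itching as unsolicited and present no solicited itching rate. This needs a look at the form and, at most, a rerun of the local-event rows.

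3. As a minor clarification, add one sentence to Section 11 stating that a diary-type symptom with onset after the diary closes on Day 8 is classed as unsolicited. This writes down the existing plain reading and changes nothing that is collected.

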11.1 DEFINITIONS

11.1.1 Adverse Event Definitions and Classifications

Adverse Event

An AE is any untoward medical occurrence in a clinical study subject administered a medicinal (investigational or non-investigational) product. An AE does not necessarily have a causal relationship with the treatment. An AE can therefore be any unfavourable and unintended sign (including an abnormal finding), symptom, or disease temporally associated with the use of a medicinal (investigational or non-investigational) product, whether or not related to that medicinal (investigational or non-investigational) product. (Definition per International Council for Harmonisation of Technical Requirements for Pharmaceuticals for Human Use [ICH].)

This includes any occurrence that is new in onset or aggravated in severity or frequency from the baseline condition, or abnormal results of diagnostic procedures, including laboratory test abnormalities.

Note: For time period of sponsor's adverse event collection, see Section 11.3.

Serious Adverse Event

A serious adverse event based on ICH and EU Guidelines on Pharmacovigilance for Medicinal Products for Human Use is any untoward medical occurrence that at any dose:

- Results in death
- Is life-threatening (the participant was at risk of death at the time of the event. It does not refer to an event that hypothetically might have caused death if it were more severe.)
- Requires inpatient hospitalisation or prolongation of existing hospitalisation
- Results in persistent or significant disability/incapacity
- Is a congenital anomaly/birth defect
- Is a suspected transmission of any infectious agent via a medicinal product
- Is medically important*

*Medical and scientific judgment should be exercised in deciding whether expedited reporting is also appropriate in other situations (other than those listed above), such as important medical events that may not be immediately life threatening or result in death or hospitalisation but may jeopardise the participant or may require intervention to prevent one of the other outcomes listed in the definition above. These should usually be considered serious.

If a serious and unexpected AE occurs for which there is evidence suggesting a causal relationship between the study intervention and the event (e.g., death from anaphylaxis), the event must be

reported as a suspected unexpected serious adverse reaction (SUSAR) (even after the study is over, if the sponsor, the independent medical reviewer, or the investigator becomes aware of them).

Unlisted (Unexpected) Adverse Event/Reference Safety Information

An AE is considered unlisted if the nature or severity is not consistent with the applicable product reference safety information. For Ad26.ZEBOV the expectedness of an AE will be determined by whether or not it is listed in the IB.

Adverse Event Associated With the Use of the Intervention

An AE is considered associated with the use of the intervention if the attribution is related by the definitions listed in Section 11.1.2.

An AE is considered not associated with the use of the intervention if the attribution is unrelated by the definitions listed in Section 11.1.2.

